11.3.1 Variables and Criteria Defining Abnormality

Clinical laboratory tests performed are listed below.

Table 22. Clinical Laboratory Tests

Category	Test Name
Haematology	Hematocrit (Hct) Hemoglobin (Hb) Glycosylated Hbc (HbA1c) White Blood Cells/Leukocytes Platelet Count/Thrombocytes
Diff. Automatic	Neutrophils (relative count) Eosinophils (relative count) Lymphocytes (relative count)
Enzymes	AST(GOT) ALT(GPT) Alkaline Phosphatase (AP) Creatine Kinase (CK) Gamma-Glutamyl Transferase (GGT/ γ -GT) Lactic Dehydrogenase (LDH) Amylase Lipase
Electrolytes	Calcium Sodium Potassium
Substrates	Glucose BUN (blood urea nitrogen) Uric acid Creatinine eGFR (estimated by CKD-EPI formula) Bilirubin Total Albumin C-Reactive Protein (high sensitive) Cholesterol, total Triglycerides LDL-Cholesterol HDL-Cholesterol
Urinalysis (Stix)	Urine Protein Urine Glucose

11.3.2 Statistical Methods

Analysis of Quantitative Laboratory Parameters (Hematology and Chemistry)

Though the protocol indicates utilizing the Rheumatology Common Toxicity Criteria (RCTC) scale for grading laboratory values, given that the National Cancer Institute Common Toxicity Criteria for Adverse Events (NCI CTCAE) scale includes a more comprehensive list of laboratory values; the lab analyses based on the NCI CTCAE scale will be presented. Changes from Baseline to each scheduled visit and to the final value in continuous laboratory parameters will be summarized with the mean, standard deviation and median. The Baseline and visit/final value means will also be presented for subjects who have both the Baseline and visit/final values (see Section 6.0 for the definition of Baseline and final values).

If there are multiple post-baseline measurements on the same day, average value will be used.

Shift Tables

Shift tables for changes from Baseline according to the normal range will be provided for each hematology and clinical chemistry parameter. Shifts from Baseline to the following endpoints will be considered: minimum value, maximum value and final value.

Categories of "low or normal" and "high or normal" will be included at Baseline in addition to the categories of "low," "normal," "high" and "missing."

If there are multiple post-baseline measurements on the same day, the last value will be used.

Potentially Clinically Important Laboratory Values

Frequencies and percentages of subjects with post Baseline lab values meeting the following criteria will be summarized. Of note, a post baseline value must be more extreme than the baseline value to be considered a potentially clinically important finding.

Table 23. Criteria for Potentially Clinically Important Chemistry Values

Chemistry Variables	Units	Definition of Potentially Clinically Important Current (Version 4) NCI CTCAE Grade 3 or Greater	
		Very Low	Very High
TBL	mcmol/L		> 3.0 × ULN
SGOT/AST	U/L		> 5.0 × ULN
SGPT/ALT	U/L		> 5.0 × ULN
Albumin	g/L	< 20	
Glucose	mmol/L	< 2.2	> 13.9
Triglycerides	mmol/L		> 5.7
Creatinine	mcmol/L		> 3.0 × ULN
Sodium	mmol/L	< 130	> 155
Potassium	mmol/L	< 3.0	> 6.0
Calcium	mmol/L	< 1.75	> 3.1
CPK	U/L		> 5.0 × ULN
Total Cholesterol	mmol/L		> 10.34
GGT			> 5.0 × ULN
ALP			> 5.0 × ULN

Note: A post baseline value must be more extreme than the baseline value to be considered a potentially clinically important finding.

Table 24. Criteria for Potentially Clinically Important Hematology Values

Hematology Variables	Units	Definition of Potentially Clinically Important Current (Version 4) Grade 3 or Greater
		Very Low
Hemoglobin	g/dL	< 8.0
Platelets count	10 ⁹ /L	< 50.0
WBC count	10 ⁹ /L	< 2.0
Neutrophils	10 ⁹ /L	< 1.0
Lymphocytes	10 ⁹ /L	< 0.5

Note: A post baseline value must be more extreme than the baseline value to be considered a potentially clinically important finding.

A separate listing will be provided that presents all of the subjects and values that are NCI CTCAE toxicity grade 3 or above. For each of these subjects, the whole course of the respective parameter will be listed. The NCI CTCAE grading is shown in [Table 25](#) below:

Table 25. NCI CTCAE Grading

Test	Grade 1	Grade 2	Grade 3	Grade 4
SGPT/ALT increased	> ULN – 3.0 × ULN	> 3.0 – 5.0 × ULN	> 5.0 – 20.0 × ULN	> 20.0 × ULN
SGOT/AST increased	> ULN – 3.0 × ULN	> 3.0 – 5.0 × ULN	> 5.0 – 20.0 × ULN	> 20.0 × ULN
GGT increased	> ULN – 2.5 × ULN	> 2.5 – 5.0 × ULN	> 5.0 – 20.0 × ULN	> 20.0 × ULN
ALP increased	> ULN – 3.0 × ULN	> 3.0 – 5.0 × ULN	> 5.0 – 20.0 × ULN	> 20.0 × ULN
TBL increased	> ULN – 1.5 × ULN	> 1.5 – 3.0 × ULN	> 3.0 – 10.0 × ULN	> 10.0 × ULN
Creatinine increased	> ULN – 1.5 × ULN	> 1.5 – 3.0 × ULN	> 3.0 – 6.0 × ULN	> 6.0 × ULN
CPK increased	> ULN – 2.5 × ULN	> 2.5 – 5.0 × ULN	> 5.0 – 10.0 × ULN	> 10.0 × ULN
Hemoglobin decreased	< LLN – 100.0 g/L	< 100.0 – 80.0 g/L	< 80.0	
Neutrophil count decreased	< LLN – 1.5 × 10 ⁹ /L	< 1.5 – 1.0 × 10 ⁹ /L	< 1.0 – 0.5 × 10 ⁹ /L	< 0.5 × 10 ⁹ /L
WBC decreased	< LLN – 3.0 × 10 ⁹ /L	< 3.0 – 2.0 × 10 ⁹ /L	< 2.0 – 1.0 × 10 ⁹ /L	< 1.0 × 10 ⁹ /L
Lymphocyte count decreased	< LLN – 0.8 × 10 ⁹ /L	< 0.8 – 0.5 × 10 ⁹ /L	< 0.5 – 0.2 × 10 ⁹ /L	< 0.2 × 10 ⁹ /L

If there are multiple post-baseline measurements on the same day, the worst value will be used.

Liver Function Tests

Additional summaries will be presented for liver function tests including ALT or serum glutamic-pyruvic transaminase (SGPT), AST or serum glutamic-oxaloacetic transaminase (SGOT), alkaline phosphatase, and total bilirubin. Each laboratory value will be categorized as follows:

- $< 1.5 \times \text{ULN}$
- $\geq 1.5 \times \text{ULN} - < 3.0 \times \text{ULN}$
- $\geq 3.0 \times \text{ULN} - < 5.0 \times \text{ULN}$
- $\geq 5.0 \times \text{ULN} - < 10.0 \times \text{ULN}$
- $\geq 10.0 \times \text{ULN} - < 20.0 \times \text{ULN}$
- $\geq 20.0 \times \text{ULN}$

Shift tables of Baseline to the maximum (relative to the normal range, i.e., the largest multiple relative to the upper limit of normal) values, and from Baseline to final value will be presented using these five categories. A listing of potentially clinically important liver function laboratory values will be provided. The listing will include all subjects who met any of the following four criteria:

- $\text{ALT} \geq 3 \times \text{ULN}$, or
- $\text{AST} \geq 3 \times \text{ULN}$, or
- Alkaline phosphatase $\geq 1.5 \times \text{ULN}$, or
- Total bilirubin $\geq 2 \times \text{ULN}$.

A listing of possible Hy's Law cases, defined as those who meet all of the following conditions will be provided:

- $\text{ALT} > 3 \times \text{ULN}$ or $\text{AST} > 3 \times \text{ULN}$
- Associated with an increase in bilirubin $\geq 2 \times \text{ULN}$
- Alkaline phosphatase $< 2 \times \text{ULN}$.

11.4 Analysis of Vital Signs and Weight

Analyses will be conducted in the Safety_A Population, the Safety_B_RR Population, and the ALL_RZB Population.

11.4.1 Variables and Criteria Defining Abnormality

The following vital sign parameters will be assessed: Systolic blood pressure [mmHg], Diastolic blood pressure [mmHg], Pulse [beats per minute], Respiratory rate [breaths per minute], Temperature [°C], Weight [kg]. The following table presents the Criteria for Potentially Clinically Important Vital Sign Findings. Of note, a post baseline value must be more extreme than the baseline value to be considered a potentially clinically important finding.

Table 26. Criteria for Potentially Clinically Important Vital Sign Findings

Vital Sign	Category	Criteria for Potential Clinically Important Vital Signs
Systolic Blood Pressure	Low Value	≤ 90 mmHg and decrease ≥ 20 mmHg from Baseline
	High Value	≥ 160 mmHg and increase ≥ 20 mmHg from Baseline
Diastolic Blood Pressure	Low Value	≤ 50 mmHg and decrease ≥ 15 mmHg from Baseline
	High Value	≥ 105 mmHg and increase ≥ 15 mmHg from Baseline
Pulse	Low Value	≤ 50 bpm and decrease ≥ 15 bpm from Baseline
	High Value	≥ 120 bpm and increase ≥ 15 bpm from Baseline

Note: A post baseline value must be more extreme than the baseline value to be considered a potentially clinically important finding.

11.4.2 Statistical Methods

Changes from Baseline to each visit and to the final value in vital sign parameters will be summarized with the mean, standard deviation and median. The Baseline and final value means will also be presented for subjects who have both the Baseline and final values (see Section 6.0 for the definition of Baseline and final values).

For baseline, if there are multiple measurements on the same day, the last measurement prior to the first dose of study drug will be used as the Baseline vital sign value. If there are multiple post-baseline measurements on the same day, average value will be used.

For systolic blood pressure, diastolic blood pressure and pulse, a listing of all subjects with any vital sign value meeting criteria for potentially clinically important values will be

provided. For each of these subjects, the whole course of the respective parameter will be listed. The number and percentage of subjects who have at least one value meeting criteria for potentially clinically important values will be provided for each selected vital sign parameter.

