5.3.2 Vital Signs

Vital signs evaluations will be performed at visits as shown in the [flow chart](#). This includes temperature, pulse rate, systolic/diastolic blood pressure and respiratory rate. Respiratory rate, pulse rate, and blood pressure will be measured after patients have been sitting comfortably for at least five minutes. Measurement of vital signs should precede blood sampling to avoid the impact of blood sampling on the vital measurements. At dosing visits vital signs evaluations will be performed pre-dose and at Visit 2 and Visit 5 additional measurements will be performed approximately 5 minutes post-dose (5 min. after last injection) and approximately 60 minutes post-dose (60 min. after last injection).

Patients should be closely monitored for signs and symptoms of hypersensitivity reactions for approximately 2 hours after the last injection at the Randomization Visit and for approximately 1 hour after the last injection at all other visits with drug administration. Hypersensitivity reactions should be treated according to medical standards. Pre-medications for further injections might be considered and will be agreed on between investigator and BI clinical monitor.

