6.0 Analysis Conventions

Definition of Baseline:

The last non-missing measure collected on or before the date of the first dose of study drug injection will be used as Baseline for summary of demographics and disease characteristics, efficacy analyses, and safety analyses in each period, with the exception that:

- The last evaluation on or prior to the first dose date of risankizumab will be used for the safety analyses for ALL_RZB populations.
- For all vital sign assessments, only assessments prior to first dose time will be considered, since vital signs are to be assessed both pre- and post-dose in some visits.

For subjects who are randomized but do not take any study drug during the study, the last non-missing measurement collected on or before the date of randomization will be used as Baseline.

Definition of Final Observation (Applicable to Safety Analyses):

Final observation for the Part A is defined as:

- The last non-missing observation collected within 105 days following the last dose of study drug in Part A for subjects who were not dosed in Part B.
- The last non-missing observation collected on or before the first dose date of study drug on or after Week 16 and within 105 days following the last dose of study drug in Part A for subjects who were dosed in Part B. For vital sign assessments, only assessments prior to the first dose of study drug injection in Part B will be included in the analysis for Part A.

Final observation in Part B and in the entire study is defined as the last non-missing observation collected within 105 days after the last dose of study drug.

Definition of Rx Days (Days Relative to the Date of First Dose of Study Drug)

Rx days are calculated for each time point relative to the date of first dose of study drug. They are defined as the number of days between the day of the first dose of study drug and the specific time point. Rx days are negative values when the time point of interest is prior to the first study drug dose day. Rx days are positive values when the time point of interest is on or after the first study drug dose day. The day of the first dose of study drug is defined as Rx Day 1, while the day prior to the first study drug dose is defined as Rx Day -1 (there is no Rx Day 0).

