For analysis in each Part (A or B), the Rx Day is calculated relative to the first dose of study drug in the specific study Part. For analysis across Part A and Part B, the Rx days are calculated relative to the date of first dose of study drug injection in Part A.

Definition of Analysis Windows

All time points and corresponding time windows are defined based on Rx Days.

For efficacy analyses, local tolerability, laboratory parameters, and vital sign variables, analysis windows are constructed using the following algorithm:

- Determine the nominal Rx day for each visit (e.g., Week 4 [4 weeks after Baseline visit] equals Rx Day 29).
- In order to include all post baseline data, the first post-baseline interval starts on the first day after the first dose of study drug (Rx Day 2).
- Determine the window around a specific nominal Rx day by adding or subtracting half of the interval between adjacent visits (e.g., days between Week 2 and Week 4 is 14). The threshold between adjacent visits is determined by splitting the interval evenly between the visits. If the resulting split is between Rx days, then the threshold is determined as the midpoint between the adjacent visits. If the resulting split is on an Rx day, then the threshold is determined as being between that Rx day and the Rx day prior to it (e.g., the split between Week 2 and Week 4 would be between Rx Days 22 and 23).
- If more than one assessment is included in a time window the assessment closest to the nominal day will be used. If there are two observations equidistant to the nominal day, the one after the nominal day will be used in analyses. If more than one assessment is included on the same day, then the worst assessment on that day will be used in analyses, except those specified in Section 11.0.

The protocol specified visits and corresponding time windows used in the efficacy analyses, local tolerability, ECG, laboratory parameters, and vital sign variables, are presented in the following tables.

Table 4. Visit Windows for PASI/sPGA and Vital Signs for Part A (ITT_A/PP_A/Safety_A Populations)

Window Label	Target Day	Time Window
Baseline	1	$\leq 1^a$
Week 4	29	[2, 43]
Week 8	57	[44, 71]
Week 12	85	[72, 99]
Week 16	113	[100, 127 ^b]

Rx Day calculated relative to the first dose of study drug. For subjects randomized but not dosed, Rx Day calculated relative to randomization.

- a. If time is collected in vital signs, restrict to records prior to the first dose of study drug.

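### By-visit vital-sign summaries omit the Visit 2 post-dose readings and average the Visit 5 ones, and the SAP does not say whether Table 26 is applied to individual readings

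*SAP*

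**What the plan says.** - **Schedule.** Protocol 5.3.2 (and Flow Chart footnote 4) takes vital signs before dosing. It adds that "at Visit 2 and Visit 5 additional measurements will be performed approximately 5 minutes post-dose", with a further set at about 60 minutes. The parameters are temperature, pulse, systolic and diastolic blood pressure, and respiratory rate. No reason is given for the extra sets. The next paragraph turns to clinical observation: "Patients should be closely monitored for signs and symptoms of hypersensitivity reactions".
- **Baseline.** SAP 6.0: "For all vital sign assessments, only assessments prior to first dose time will be considered". Footnote a of Tables 4 and 14 repeats the restriction.
- **Day count and windows.** SAP 6.0: "The day of the first dose of study drug is defined as Rx Day 1", and "the first post-baseline interval starts on the first day after the first dose of study drug (Rx Day 2").
- **Same-day rule.** The general rule in SAP 6.0 is to take the worst value, unless Section 11.0 specifies otherwise. For vital signs SAP 11.4.2 does: "If there are multiple post-baseline measurements on the same day, average value will be used".
- **Flagged values.** SAP 11.4.2 lists every subject with a systolic, diastolic or pulse value that meets Table 26, shows that subject's full series for the parameter, and counts subjects with one or more such values.
- **Contrast with laboratory data.** SAP 11.3.2 gives three same-day rules: the average for change summaries, the last value for shift tables, and the worst value in the part on potentially important and graded values.

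**The concern.** Readings timed at 5 and 60 minutes after an injection are informative mainly against the reading taken just before it. The SAP plans no such comparison. In the by-visit summaries one set has no place and the other is blended with its own pre-dose value.

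Week 4 is also the only Part A by-visit value into which scheduled post-injection readings enter, so it is not strictly comparable with the other weeks. Week 16 is expressly limited to records before that visit's dose (Table 4, footnote b).

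What is at stake is how completely the report describes short-term vital-sign changes. Visit 5 is of particular interest, because only risankizumab or its placebo is injected there (Protocol Table 4.1.4: 2). It allows a blinded comparison of active with placebo injection.

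**Working it through.** **1. Reproduce the windows.** The nominal Part A days are 29, 57, 85 and 113, and the next visit is Day 141. The midpoints are (29+57)/2 = 43, (57+85)/2 = 71, (85+113)/2 = 99 and (113+141)/2 = 127. Starting at Day 2 and placing each split after the midpoint day, as the SAP's worked example does, gives [2, 43], [44, 71], [72, 99] and [100, 127]. These match Table 4. The SAP's worded tie rule would move each split one day earlier, but the lower limit of Day 2 stays the same.

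**2. Place the readings.**
- Visit 2 post-dose readings are on Rx Day 1. They are not baseline, which is pre-dose only, and they precede Day 2. They fall in no window of Table 4. Table 14 (ALL_RZB) has the same structure.
- Visit 5 is on Day 29 ± 3, that is Days 26 to 32, which lies wholly inside [2, 43]. All three readings share one day and are averaged.

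**3. Count.** With about 600 patients randomised, 600 × 2 = 1,200 Visit 2 post-dose readings per parameter lie outside every by-visit window. Up to a further 1,200 at Visit 5 are averaged with the pre-dose reading.

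**4. Dilution.** If two readings equal the pre-dose value b and the third is b + D, the mean is (3b + D)/3 = b + D/3.

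**5. Effect on Table 26, if it were applied to the daily average.** The readings here are assumed. Take a baseline and Visit 5 pre-dose systolic pressure of 120, with 85 at 5 minutes and 118 at 60 minutes. The mean is (120 + 85 + 118)/3 = 107.7. Low systolic requires a value of 90 or less and a fall of at least 20. The reading of 85 qualifies (a fall of 35) and the mean does not.

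With the other two readings at an assumed baseline b and a cut-off c, the third must reach 3c − 2b for the mean to qualify:

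| Criterion | Assumed b | Cut-off c | Single reading needed | Needed if averaged (3c − 2b) |
|---|---|---|---|---|
| Low systolic | 120 | 90 | 90 | 270 − 240 = 30 |
| High systolic | 130 | 160 | 160 | 480 − 260 = 220 |
| High diastolic | 80 | 105 | 105 | 315 − 160 = 155 |
| High pulse | 72 | 120 | 120 | 360 − 144 = 216 |

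The accompanying change-from-baseline condition is met in each row.

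**6. Is Table 26 applied to averages?** The SAP does not settle this. In favour of individual readings, the listing and count refer to any qualifying value and mention neither windows nor daily averages. In favour of averages, averaging is the only same-day post-baseline rule given for vital signs, whereas the laboratory section has a separate worst-value rule. Table 26 also asks for a post-baseline value, and the SAP does not say whether a Day 1 post-dose reading counts as one. Respiratory rate and temperature have no Table 26 criteria, so the question does not arise for them.

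**The case against.** A reader might infer that the post-dose readings are lost, or that a reaction to the first dose could not appear anywhere in the report. The documents do not support that.

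- On its plain wording, the Table 26 listing and count can take in a single 5-minute systolic, diastolic or pulse reading from either visit. The listing then shows that subject's full series.
- The Rx Day 2 start belongs to the by-visit window algorithm. A Day 1 post-dose reading does come after the pre-dose baseline. The Final Observation in SAP 6.0 is not tied to these windows either.
- Vital-sign changes that the investigator judges clinically relevant are recorded as adverse events (Protocol 5.3.7). SAP 11.2.1 includes Day 1 events that start after dosing, and Table 21 names hypersensitivity and anaphylactic reaction.

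A reader might also take these readings to be the plan's stated tool for detecting injection reactions. That link is an inference from the adjacent hypersensitivity text. Nor do they cover the first two active doses in both arms: the adalimumab arm's second active dose is at Week 1, where no vital signs are scheduled, and at Visit 5 that arm receives only risankizumab placebo. Patients who switch at Week 16 have no scheduled post-dose readings at their first risankizumab dose.

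Finally, Protocol 7.3.4 promises only a descriptive comparison with pre-treatment findings, so no promised table is missing.

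All of this stands, and it limits the point. It does not answer the gap in the by-visit summaries, the averaging at Week 4, the silence on how Table 26 is applied, or the lack of criteria for respiratory rate and temperature. Adverse event reporting depends on investigator judgement and does not replace a summary of scheduled measurements.

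**Conclusion.** The point holds for the by-visit summaries. Visit 2 post-dose readings enter none of them, and the Visit 5 readings are merged into a Week 4 value in which a change at one reading appears at one third of its size. Both follow from stated rules, and the window boundaries reproduce exactly.

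For the Table 26 output the finding is ambiguity, not omission. Individual systolic, diastolic and pulse readings may be captured, but a programmer could also reasonably use the daily average. The threshold shifts in the working apply only under that second reading and rest on assumed baselines. For respiratory rate and temperature, Visit 2 post-dose readings have neither a by-visit summary nor a criteria-based listing.

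The count of 1,200 assumes 600 treated patients with complete readings. Severity is low to moderate and confined to descriptive safety reporting. Efficacy tests, alpha and sample size are unaffected.

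**What to change.** Amend SAP 6.0 and 11.4.2 as follows:

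1. Use the pre-dose reading at each visit for by-visit change from baseline, so that Week 4 is on the same footing as the other weeks.
2. State that Table 26 is applied to each individual reading after the first dose, including the Day 1 post-dose readings, and not to the daily average. Any day whose average qualifies also has a single reading that qualifies, so no flagged day is dropped.
3. Add one descriptive table of change from the same-visit pre-dose reading at 5 and 60 minutes, for Visits 2 and 5, by treatment in Safety_A. It should cover all the vital-sign parameters, including respiratory rate and temperature.

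The cost is SAP wording and one extra table from data already scheduled for collection. No trial procedure changes.
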